If the patient is interested in the study, a member of the research team will approach him/her for enrollment. Consent process will be conducted face to face. Participants will be provided a written consent form in person. No waiting time is expected between informing the prospective participant and obtaining the consent.

Consent will take place during patients' pre-operative clinic visit. If patients are interested and there is not enough time to consent the patient in urology clinic, study information will be sent home with the patient and the patient will then be consented before their surgery in a private room (pre-operative room). Pre-operative room provides 1-1 1/2 hours of time. This should be ample time to conduct the consent process before surgery anesthesia.

All information about the study will be provided, and ample time will be made available for the participants to consider participation in the study.

Patient Randomization

Patients will be randomized (ratio 1:1) at the time of enrollment to be treated with either the holmium laser with Moses or the thulium laser. We will use Permuted Block Randomization (stratified by stone size 3 - 10 mm or 11-20 mm) (block size 4).

Study Procedures

1. The study team members review patients' medical record during patients' pre-operative clinic visit to see whether patients meet inclusion/exclusion criteria.
2. If patients meet the inclusion criteria, a study team member who is affiliated with the patient's clinical care (e.g., the surgeon) will initially approach the patients who are scheduled for laser lithotripsy treatment of urinary stones. (i.e., informed that there's a research study they may be eligible for, and asked if they want to learn more about it).
3. If the patient is interested in the study, a member of the research team will approach him/her for enrollment.
4. Patients will be asked to fill out a WISQOL short form at their pre-operative visit. This is standard of care for all stone patients in clinic.

5. Patients' total stone size (pre-operative CT) will be calculated and divided into two groups. Those with stones 3-10 mm and those with stones 11-20 mm. They will then be randomized to either the holmium laser with Moses or the thulium laser (randomization ratio 1:1) group.

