6. Patients will undergo stone surgeries with the laser that they are randomized to. A 200 micron fiber will be used with both machines. The patient's stone(s) will be treated in accordance with our routine clinical practice of fragmenting stone into small pieces (≤ 2 mm). One stone fragment will be collected for stone analysis if the patient does not already have a stone analysis on file (this is also standard of care). The faculty surgeons will perform all surgeries. We are unable to blind the surgeon to the laser used as the laser fibers and laser machines appear and sound different.
7. Procedural time as well as other information (see study design for the detail information) is collected.
8. After surgery, the patients will all have at least an abdominal x-ray within 1 month of surgery, if a CT scan has not already been completed(this is the standard of care). They will also be asked to fill out a WISQOL short form at their one-month follow up appointment. Otherwise, they will continue on our normal postoperative pathway. Postoperative complications will be collected.

Comparison of usual care and study procedures

Compared with our routine care, the only interventions imposed on subjects as a result of this study are (1) pre-procedural randomization to laser lithotripsy with either holmium laser with Moses or thulium laser, and (2) the use of patient & surgery information collected in describing our results. All the other activities are part of our routine clinical practice.

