Participation in the study will require a pre-operative CT abdomen without contrast, which is standard of care, as well as at least an abdominal x-ray post operatively which is also standard of care. Four surgeon will perform the ureteroscopy (i.e., [name], [name], [name], [name], and [name]). During surgery, patients' stones will be treated in accordance with our routine clinical practice of fragmenting stones into small pieces (<2 mm). Surgeons will use a 200 micron fiber for both the holmium laser with Moses and the thulium laser, but they will have the discretion to switch to a different fiber (ex. 150 micron thulium fiber) if they feel it is necessary during the case (if the surgeon changes the fiber during the surgery, the data will be analyzed separately). A stone fragment will be collected for stone analysis if the patient does not have one on file. This is our standard of care suggested by AUA guideline.^x All patients enrolled will undergo routine post-operative follow up including clinic appointments and imaging evaluation (with at least an abdominal x-ray). An abdominal x-ray is used for follow up of nephrolithiasis and provides significantly less radiation, and it is our routine care. However, if the patient already has a CT completed by the follow-up visit, an x-ray is not needed. WISQOL short form will be administered during the pre-operative appointment and at the post-operative appointment, which is standard practice in our clinic.

Withdrawal of participants

Patients can withdraw anytime. Once they decide to withdraw, they will continue their standard clinical care with us. We will continue to collect patients' information from patients' medical records for their routine medical care.

Study Intervention

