Since we have 5 surgeons participating in this study, we will use university-based cloud service (such as OneDrive) to temporarily save the enrollment log. Study team member will use their Net ID to access the enrollment log. The enrollment log is completely deidentified. Only participant ID (such as 101, 102) and the laser each participant is randomized to are saved in the enrollment log. Once we complete data collection, we will permanently delete it from the cloud.

Share of results

NCT04963062
Protocol 2021-0695

Some of the information collected for this study will go in the patient's medical record. This includes the results of the one-month post-operative image, stone analysis, stone surgery, and all clinic visits information as these are being conducted as standard of care. All other information from research specific procedures will NOT go in the patient's medical records.

We only publish aggregated results. No individual results will be shared. We will not share the data with outside institutions.

Economic burden to participants

This study does not place financial burden to patients. The study interventions are our routine clinical practice to treat stones. It will be same as they are not involved in this study.

The cost of the two laser treatments are equivalent.

Data Analysis

The data collected will be analyzed as an intention-to-treat analysis. Statistical analyses will include T-test and, if appropriate, Chi-square tests (e.g., for categorical data), and two-way MANOVA. Patient demographics and stone characteristics will be summarized as appropriate as continuous variables (mean and standard deviation) or categorical variables (frequency, percentage). To compare the two groups, continuous variables such as procedural time, total OR time, WISQOL etc., will be analyzed using T test and two-way MANCOVA (stratified by stone size 3 - 10 mm or 11-20 mm). The surgeon will be controlled as a covariate. Categorical variables such as stone free rate will be analyzed using chi-square.

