We plan to enroll 164 patients in this study. Patients will be stratified into two groups according to their stone size (3-10 mm or 11-20 mm) and then randomized to either holmium laser with Moses or thulium laser. The stone size is defined as the largest stone size (largest diameter on pre-operative CT), if patients have multiple stones. Previous literature suggested stone size is associated with operative time.^{ix} A significance level of 0.05 will be used with a two-sided two-sample equal-variance t-test. Group sample sizes of 33 and 33 achieve 80% power to detect a significant difference between the means when the mean difference is 4.6 minutes with a standard deviation of 6.5 minutes. We also decide to increase the sample size by 25% (41 patients per group). This will allow for the possibility that the randomization scheme is intra-operatively abandoned for some reason (e.g., equipment failure), that the planned procedure was unable to be completed for some reason, as determined by the surgeon in

charge of the case, and/or that the patient – after his/her procedure – wishes to withdraw from the study and exclude his/her information from our analysis.

ⁱ Scales CD Jr, Smith AC, Hanley JM, Saigal CS; Urologic Diseases in America Project. Prevalence of kidney stones in the United States. *Eur Urol*. 2012 Jul;62(1):160-5.

ⁱⁱ Geraghty RM, Jones P, Somani BK. Worldwide Trends of Urinary Stone Disease Treatment Over the Last Two Decades: A Systematic Review. *J Endourol* 2017 Jun;31(6):547-556.

ⁱⁱⁱ Assimos D, Krambeck A, Miller NL, et al: Surgical Management of Stones: American Urological Association/Endourological Society Guideline, PART II. *J. Urol.* 2016.

^{iv} Andreeva V, Vinarov A, Yaroslavsky I, et al. Preclinical comparison of superpulse thulium fiber laser and a holmium:YAG laser for lithotripsy. *World J Urol*. 2020 Feb;38(2):497-503.

^v Ventimiglia E, Doizi S, Kovalenko A, et al. Effect of temporal pulse shape on urinary stone phantom retropulsion rate and ablation efficiency using holmium:YAG and super-pulse thulium fibre lasers. *BJU Int*. 2020 Jul;126(1):159-167.

^{vi} Bagrodia A, Gupta A, Raman JD, et al. Predictors of cost and clinical outcomes of percutaneous nephrolithotomy. *J Urol*. 2009 Aug;182(2):586-90.

^{vii} Schuster TG, Hollenbeck BK, Faerber GJ, Wolf JS Jr. Complications of ureteroscopy: analysis of predictive factors. *J Urol*. 2001 Aug;166(2):538-40.

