### **Data Analysis Plan**

Statistical analyses include using appropriate categorical/continuous and parametric/non-parametric statistical test. Patient demographics (such age, gender, race ethnicity) and stone characteristics (such as stone volume, location, density) will be summarized as appropriate as continuous variables (mean and standard deviation) or categorical variables (frequency, percentage). To compare the two groups, procedural time, laser time, ablation speed, ablation efficiency, total energy used, are analyzed using Wilcoxon test. The score of quality of life survey and laser evaluation survey are analyzed using MANOVA. Complication rate is analyzed using chi-square. Statistical significance is set as two-tailed p value < 0.05 and data are analyzed using SPSS 25.

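### The protocol says surgeon will be controlled for, but the SAP tests procedural time with a Wilcoxon test that has no surgeon or stone-size term: the test stays valid, but a promised adjustment and some precision are lost.

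*SAP*

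**What the plan says.** - **Protocol, Data Analysis.** Continuous outcomes, with procedural time named first, "will be analyzed using T test and two-way MANCOVA (stratified by stone size 3 - 10 mm or 11-20 mm". The next sentence reads "The surgeon will be controlled as a covariate". The section does not say whether the T test or the MANCOVA is primary.
- **Protocol, Patient Randomization.** "We will use Permuted Block Randomization (stratified by stone size 3 - 10 mm or 11-20 mm) (block size 4". Surgeon is not a stratum.
- **Protocol, sample size (end of Data Analysis).** "A significance level of 0.05 will be used with a two-sided two-sample equal-variance t-test". The inputs are a 4.6-minute difference, an SD of 6.5 minutes, 33 per group and 80% power. It does not say whether 6.5 minutes includes differences between surgeons.
- **Protocol, number of operators.** The comparison of usual care and study procedures says "Four surgeon will perform the ureteroscopy", followed by five redacted names. The data management section says "Since we have 5 surgeons participating in this study".
- **SAP, Data Analysis Plan.** "procedural time, laser time, ablation speed, ablation efficiency, total energy used, are analyzed using Wilcoxon test". No surgeon term or stone-size stratum is named for any outcome. This is the only SAP text available for review.

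**The concern.** Procedural time runs from insertion to removal of the ureteroscope, so it partly measures how fast the operator works. The investigators chose surgeon as the covariate to control, which suggests that they expect operators to differ. Because allocation is not stratified by surgeon, the analysis is the only planned place where surgeon differences could be removed from the comparison, and the SAP's test does not remove them.

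Two things are at stake. Spread between surgeons stays in the error term, so the laser comparison may be less precise than the same data allow. And the two documents now support different analyses of the primary outcome, with nothing to say which one governs.

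**Working it through.** **1. Reproduce the planned power.** Inputs from the protocol: difference 4.6, SD 6.5, 33 per group, two-sided 0.05, equal-variance t-test.

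- Noncentrality = 4.6 / (6.5 × √(2/33)) = 4.6 / 1.600 = 2.875, with 64 df.
- Exact noncentral-t power = 80.8% (79.6% at 32 per group). The stated 33 per group for 80% is reproduced.

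**2. Add surgeon to the model.** The share of variance due to surgeon, ρ, is not in the documents and is assumed here at 0 to 30%. Further assumptions: 6.5 minutes is the total SD, and there are five surgeons, hence four extra parameters.

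- Residual SD = 6.5 × √(1 − ρ).
- Effective n per group = 33 × (1 − 4/66) = 31, which allows for chance imbalance in surgeon mix.
- Error df = 64 − 4 = 60.

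| ρ | Residual SD (min) | Noncentrality | Adjusted power | Change from 80.8% |
|---|---|---|---|---|
| 0 | 6.50 | 2.786 | 78.3% | −2.5 points |
| 10% | 6.17 | 2.937 | 82.4% | +1.6 |
| 20% | 5.81 | 3.115 | 86.5% | +5.7 |
| 30% | 5.44 | 3.330 | 90.6% | +9.8 |

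Adjusted and unadjusted power are equal at ρ of about 6%.

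**3. Check against the SAP's own test.** A simulation used 66 patients in one size band, blocks of four not stratified by surgeon, five surgeons with equal expected caseloads, and 6,000 runs.

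- At ρ of 10%, 20% and 30%, Wilcoxon power was 79.6%, 78.5% and 77.2%.
- With surgeon terms in a linear model it was 82.7%, 87.1% and 90.8%.
- With no true difference between lasers, the Wilcoxon test rejected in 4.8% to 5.1% of runs over ρ from 0 to 30%. Omitting surgeon does not inflate type I error.

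**4. Pooled over both size bands.** The SAP compares the two laser groups and mentions no size bands. With 2 × 33 = 66 per arm and the same SD:

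- Unadjusted noncentrality = 4.6 / (6.5 × √(2/66)) = 4.065; power 98.1%.
- Adjusted (effective n = 66 × (1 − 4/132) = 64 per arm, 126 df): 98.7%, 99.3% and 99.7% at ρ of 10%, 20% and 30%. The gain is 0.6 to 1.6 points.

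**5. If 6.5 minutes is instead the within-surgeon SD.** The total SD is then 6.5 / √(1 − ρ) = 6.85, 7.27 and 7.77 minutes, and unadjusted t-test power at 33 per group is 76.6%, 71.6% and 65.9%. The protocol does not say which SD it means.

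**The case against.** The strongest reply is that nothing is invalid. Under randomisation surgeon is not a systematic confounder, and the simulated type I error supports this. That stands in full.

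A reader might go further and infer that a fast surgeon who happens to do more cases with one laser adds an error on top of the reported uncertainty. It does not. With equal caseloads, the spread of the laser difference due to surgeon mix is √ρ times the unadjusted standard error. At 41 per group that standard error is 6.5 × √(2/41) = 1.44 minutes, so the surgeon part is 0.45 minutes at ρ of 10% and 0.79 at 30%. This is a component of the standard error already in the test, so setting it against the 4.6-minute target as extra error would count it twice.

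It can also be said that the protocol itself lists a T test, which takes no covariate, and sizes the trial on one. An unadjusted test therefore falls within the protocol's plan, and what the SAP omits is the adjusted analysis alongside it. This also stands. It narrows the point but does not remove it: the covariate sentence is explicit, and neither document says which analysis is primary.

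Finally, the size depends on a surgeon share that no passage supplies, and the larger gains need 20% to 30%. That is correct, and it is why a range is shown. Lack of blinding and visual judgement of fragment size do not strengthen the case, because a surgeon term would not cure either. The four-versus-five discrepancy may be a slip, since five redacted names follow the word four.

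**Conclusion.** The point holds as a loss of a promised adjustment, of precision and of consistency between protocol and SAP. It is not a finding of bias or of an invalid test.

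If 6.5 minutes is the total SD, the planned 80% is intact under the t-test and only a possible gain is forgone. Within one size band this is about 2, 6 and 10 points at surgeon shares of 10%, 20% and 30%, with a break-even near 6% and a cost of about 2.5 points at zero. For a comparison pooled over bands at the same SD, it is under 2 points.

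A reader might infer from step 5 that the trial is underpowered without adjustment. The documents do not support that, because they never describe 6.5 minutes as a within-surgeon SD. The surgeon share, the five equal caseloads and the reading of 6.5 minutes are all assumptions. The reading of the SAP rests on its Data Analysis Plan alone.

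**What to change.** - In the SAP, name one primary analysis of procedural time that includes laser, surgeon as a fixed factor, and the stone-size randomisation stratum.
- Fix its scale before outcome data are seen. A linear model in minutes would serve, as would a rank test stratified by surgeon and stone size (van Elteren). Do not leave the choice between minutes, logs and ranks until skewness has been inspected; a log scale would also change the target from a difference in minutes to a ratio.
- Keep the unadjusted Wilcoxon test as a sensitivity analysis.
- Align the protocol's Data Analysis section so that it names the same primary analysis.
- Reconcile the four and five surgeons so that the factor has defined levels.

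The cost is wording in the SAP and protocol, and about four degrees of freedom for surgeon. Members of the study team perform the procedures, so the operator should be identifiable for every case and no new patient data are needed. If surgeons hardly differ, the adjusted analysis is slightly less powerful, by about 2.5 points at worst in the 33 versus 33 comparison. Stratifying randomisation by surgeon is not required for this fix.

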UW, Department of Urology only

Background and Significance

The incidence of urinary tract stone disease is increasing. According to the National Health and Nutrition Examination Survey, as of 2012, 10.6% of men and 7.1% of women in the United States are affected by renal stone disease.ⁱ This has led to an increased demand on Urologists for efficient and safe surgical treatment of stone disease. Over the past two decades, ureteroscopy with laser lithotripsy has become the treatment of choice for most ureteral and renal stones globally.ⁱⁱ The holmium laser is considered the gold standard for laser lithotripsy.ⁱⁱⁱ Holmium laser lithotripsy with Moses and the thulium laser are new technologies meant to improve the efficiency of laser lithotripsy. Both are FDA approved treatment modalities for stone disease. Two in vitro studies have compared Moses versus thulium and shown that thulium has higher ablative volumes than the holmium laser with Moses, but no clinical trials have compared the two treatment modalities.^{iv,v} In this study, we are going to conduct a prospective, randomized clinical trial to determine whether there is a difference in procedural time, intraoperative parameters or stone free rate between the Holmium laser with Moses and the thulium laser. This is significant as this may lead to shorter overall operative times, which may result in decreased operative costs and complications.^{vi,vii}

Study Objectives

The primary objective of this study is to compare the procedural time to acceptable stone fragmentation during clinical use of the holmium laser with Moses and the thulium laser. Our hypothesis is that the thulium laser will have decreased procedural time compared to the holmium laser with Moses. Secondary outcomes will include intra-operative parameters and post-operative parameters. Our clinical practice is to treat urinary stones until the stone is reduced to fragments \leq 2 mm in size. This is determined by using the laser fiber (A 200 micron fiber will be used with both groups), to visually estimate the size of the resultant fragments.^{viii}

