The secondary objective is to compare the primary and secondary outcomes when stratified by stone size. This will allow us to explore the efficiency between Moses and thulium laser on treating large vs. small stones. Previous literature suggested that stone size was associated with operative time.^{ix} Patients will be separated based on the size of their stones: 3-10 mm or 11-20 mm and then randomized to holmium laser with Moses or thulium laser. Patients will be randomized into the groups by a ratio of 1:1.

Research Design and Methods

This study will be a randomized trial comparing ureteroscopy with laser lithotripsy with the Lumenis® Pulse™ P120H holmium laser system with the Moses technology (holmium laser with moses) versus the Soltive™ SuperPulsed Laser System with the thulium fiber laser technology (thulium laser). The primary objective is to compare the procedural time (minutes). We will keep strict timing from the minute the ureteroscope is inserted into the patient to the time the ureteroscope has been removed. The following information will be collected as secondary outcomes: (1) stone free rate; (2) total operative time (minutes); (3) fragmentation/dusting time (minutes, total time to fragment the stone, including the laser was in use and time of pedal pauses); (4) lasing time (minutes, time the laser was in use, not including pedal pauses); (5) total energy used (kilojoules, kJ); (6) laser efficiency (mm per minute); (7) number of times the laser pedals are pressed (left, right, and total pedal presses); (8) stone analysis; (9) complications; (10) quality of life survey (WISQOL short form) both pre-operatively and post-operatively and (11) physician evaluation of the laser. Physicians will complete a one page survey at the end of the case evaluating the laser (survey included as attachment). A total of 3 clinic visits (i.e., pre-operative visit, the stone surgery, and one post-operative visit) will be needed for this study. Stone parameters (i.e. size, location, Hounsfield units, presence of hydronephrosis, stone volume), demographic information, co-morbidities, and post-operative parameters will be collected from the medical record.

Number of Participants

NCT04963062
Protocol 2021-0695

Approximately 164 patients will be enrolled (see Data Analysis for sample size justification).

Inclusion Criteria

1. Patients at least 18 years of age, and less than 89 years old.

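### The visible SAP text gives the primary outcome a Wilcoxon test but no effect estimate or confidence interval, so the result cannot be read against the 4.6 minutes used to size the trial

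*SAP*

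**What the plan says.** - **SAP, Data Analysis Plan, primary outcome:** "procedural time, laser time, ablation speed, ablation efficiency, total energy used, are analyzed using Wilcoxon test". The decision rule is "Statistical significance is set as two-tailed p value < 0.05". No stratum or surgeon adjustment is mentioned for this test. The mean-and-SD summary in the same section covers demographics and stone characteristics, not procedural time.
- **Protocol, Data Analysis, comparison of groups:** procedural time goes to a t-test and a two-way MANCOVA by stone-size band, with surgeon as a covariate. No interval is named here either.
- **Protocol, Data Analysis, sample size:** "A significance level of 0.05 will be used with a two-sided two-sample equal-variance t-test". The planning assumption is "the mean difference is 4.6 minutes with a standard deviation of 6.5 minutes", for which 33 per group are said to give 80% power. The 33 is raised by 25% to 41 per group, and planned enrolment is 164.
- **Protocol, Background and Significance:** the stated value of the comparison is that "this may lead to shorter overall operative times, which may result in decreased operative costs and complications".

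**The concern.** The design and the rationale are both about minutes: the trial is sized on a difference in means, and its value lies in time saved. A Wilcoxon p-value is not in minutes. It says whether one laser's times tend to rank below the other's. If the two distributions differ in shape or spread, it does not test a difference in means, although nothing in the documents shows that they will differ in that way.

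Two conclusions are at stake. A significant result could reflect a saving well under the planned 4.6 minutes or one well over it. A non-significant result could mean that 4.6 has been ruled out, or that the data were too variable to say. The p-value alone separates neither pair.

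If the estimate is left open, the choice among mean, median or shift, adjusted or not, can be made after the data are seen. The protocol says that the surgeons cannot be blinded, so the estimate is better fixed in advance.

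**Working it through.** **Inputs.** Protocol, Data Analysis: difference 4.6 min, SD 6.5 min, two-sided alpha 0.05, 80% power, 33 per group raised by 25% to 41, total 164. Protocol, Patient Randomization: 1:1, stratified by two stone-size bands.

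**1. The plan's own figure.** By the normal approximation, n = 2 × (1.960 + 0.842)² × 6.5² / 4.6² = 31.3, so 32 per group. The exact t calculation gives 32.3, so 33, with power 80.8%. Then 33 × 1.25 = 41.25, taken as 41, and 4 × 41 = 164. The figure reproduces. It fits two lasers by two size bands: 41 per laser within a band, or 82 per laser overall if the bands fill equally.

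**2. Smallest observed difference that is significant.** This is t(0.975, 2n − 2) × SD × √(2/n), which is also the half-width of the 95% CI for a difference in means. At SD 6.5:

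| Per arm | SE (min) | Smallest significant difference (min) | 95% CI at that point |
|---|---|---|---|
| 82 (all enrolled) | 1.015 | 2.00 | 0 to 4.0 |
| 66 (2 × 33) | 1.132 | 2.24 | 0 to 4.5 |
| 41 (one stratum) | 1.436 | 2.86 | 0 to 5.7 |
| 33 (one stratum, before inflation) | 1.600 | 3.20 | 0 to 6.4 |

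These are t-test figures. For normal data the Wilcoxon equivalent is larger by 1/√(3/π): 2.00 becomes 2.05 at 82 per arm. The choice of test hardly moves the threshold.

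**3. Between-stratum spread.** If 6.5 is the SD within a size band, an unadjusted pooled comparison has SD √(6.5² + (gap/2)²), where gap is the difference between the two band means. The documents give no gap, so these are assumptions:
- Gap 10 min: SD √(42.25 + 25) = 8.2, threshold about 2.5 min.
- Gap 20 min: SD √(42.25 + 100) = 11.9, threshold about 3.7 min.

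Adjusting for stratum removes this added spread and brings the half-width back to about 2.0 min.

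**4. What the p-value hides** (82 per arm; savings written as positive numbers).
- *Both significant, SD 6.5.* A saving of 2.5 min has CI 0.5 to 4.5, which excludes 4.6. A saving of 5.0 min has CI 3.0 to 7.0, which includes it.
- *Both non-significant.* A saving of 1.5 min has CI −0.5 to 3.5 at SD 6.5, which rules out 4.6. At the assumed SD of 11.9 it has CI −2.2 to 5.2, which does not.

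**5. Simulation.** With normal data, 82 per arm, SD 6.5, a true saving of 2.0 min and 3,000 runs, the Wilcoxon test favoured thulium in 48% of runs. Among those, the CI for the mean difference excluded 4.6 in 44%, and the observed saving reached 4.6 in about 1%.

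**The case against.** Four objections have force.

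- **The threshold is not caused by Wilcoxon.** A reader might infer that the rank test lets thulium be called faster on about 2 minutes. The documents do not support that. The protocol's t-test gives the same figure, and even the planned 33 per group is significant at 3.2 min. A threshold below the planning difference is normal in a trial with 80% power.
- **Two minutes is the most favourable case.** It needs 82 against 82 and a pooled SD of 6.5. Results that are significant and also exclude 4.6 lie only between 2.00 and 2.60 min at 82 per arm and between 2.24 and 2.36 at 66, and none exist at 41. At 82 per arm the window closes once the pooled SD passes 2.3 / (1.975 × √(2/82)) = 7.5. The protocol itself links stone size to operative time, so a larger pooled SD is plausible.
- **4.6 minutes is only a planning assumption.** It appears in the sample-size paragraph alone and is never called clinically important. Nothing in the documents supports calling 2 minutes clinically small.
- **Silence is not prohibition.** The SAP names tests and does not forbid estimates. Part of the SAP is not in the text available, so the gap can be asserted only for the visible text.

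All four limit the size and wording of the point. None supplies the missing estimate. Authors may well report medians, but two group medians carry no interval for their difference, and the choice would be made late.

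**Conclusion.** The point holds for the visible text. The SAP gives the primary outcome an unadjusted rank test at p < 0.05, without an estimate or interval. The protocol names different analyses, also without an interval. So the primary result, followed as written, cannot be placed relative to the 4.6 minutes on which the trial was sized.

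The scale depends on assumptions: the smallest significant difference is about 2.0 min (82 per arm, SD 6.5), 2.9 min (one stratum of 41 per arm) or up to about 3.7 min (82 per arm, assumed pooled SD 11.9). All lie below 4.6. At the two larger thresholds a just-significant interval still contains 4.6. The point does not rest on the narrow window where it is excluded, because without an interval no result can be located at all.

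This should be changed. It does not invalidate the design.

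**What to change.** In the SAP's Data Analysis Plan:

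1. Make the primary result the thulium-minus-Moses difference in mean procedural time, in minutes, with a 95% CI. Take it from a model adjusted for stone-size stratum and surgeon, with a robust or bootstrap CI because times may be skewed. A saving with thulium then has a negative sign.
2. Reconcile this with the protocol's t-test and MANCOVA, so that both documents name one primary analysis.
3. If the Wilcoxon test is kept, report the Hodges-Lehmann shift with its 95% CI beside it.
4. Show the interval next to 4.6 minutes, labelled as the planning assumption and not as a clinically important difference.

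The cost is a short edit to the SAP, a matching line in the protocol and a little more output. No new data are needed and patient care does not change. The downside for the authors is that a small but significant saving will be visible as small.

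### Protocol and SAP prescribe different analyses of procedural time, and neither fixes the deciding test or says whether the sample size is per stone-size band

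*SAP*

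**What the plan says.** There is one primary outcome, procedural time, and one primary objective, its comparison between lasers (Protocol, Study Objectives; Research Design and Methods). Comparison by stone size is the secondary objective. Randomisation is stratified by band, 3–10 mm and 11–20 mm.

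On the analysis of procedural time:

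- Protocol, Data Analysis: "continuous variables such as procedural time, total OR time, WISQOL etc., will be analyzed using T test and two-way MANCOVA". The MANCOVA is by size band, with surgeon as a covariate.
- Protocol, Data Analysis, sample size: "A significance level of 0.05 will be used with a two-sided two-sample equal-variance t-test".
- SAP, Data Analysis Plan: "procedural time, laser time, ablation speed, ablation efficiency, total energy used, are analyzed using Wilcoxon test". Procedural time is one of five measures in that list and is not marked as primary. The SAP also says: "Statistical significance is set as two-tailed p value < 0.05".

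On size: "Group sample sizes of 33 and 33 achieve 80% power" when the "mean difference is 4.6 minutes with a standard deviation of 6.5 minutes". This is raised by 25% to 41 per group, and "We plan to enroll 164 patients in this study". The documents do not define group in that calculation.

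**The concern.** The two documents cannot both be followed as the primary analysis. The t-test and the Wilcoxon test as named use neither size band nor surgeon; the MANCOVA uses both. No available text ranks the tests, says that the SAP replaces the protocol, or gives a rule for when they disagree. The SAP's opening sentence leaves the choice between parametric and non-parametric tests to what is appropriate, without a criterion.

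The choice could therefore be made after the results are known. The surgeons are not blinded, and the protocol's hypothesis favours thulium, so it should be closed in advance. The protocol itself says that stone size is associated with operative time, and that is the condition under which adjusted and unadjusted tests give different answers.

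**Working it through.** **1. The plan's own figure.** Inputs from the Protocol, Data Analysis: difference 4.6 min, SD 6.5 min, two-sided 0.05, 80% power.

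- Normal approximation: n = 2(1.960 + 0.842)² × (6.5/4.6)² = 31.3, so 32 per group.
- Exact noncentral t: n = 32.3, so 33 per group, with power 80.8%. The figure is reproduced.
- Inflation: 33 × 1.25 = 41.25, taken as 41.
- If a group were a whole laser arm, the total would be 2 × 41 = 82. The plan enrols 164 = 4 × 41, which fits two lasers in each of two bands. This is an inference; the text does not say it.

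**2. Type I error if any significant result could be claimed.** Null simulation: 6,000 trials per scenario, 41 or 33 per arm per band, normal or lognormal times. Assumptions not in the documents: band gap 0, 6.5 or 13 min; five surgeons with effects up to ±3.25 min; lognormal shape 0.6; MANCOVA represented by a univariate model for procedural time with laser, band and surgeon. Monte Carlo error is about 0.3–0.5 points.

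- Any of the three overall tests (t, adjusted model, Wilcoxon): 4.7–7.9%.
- Either of the two band t-tests: 8.8–10.2% (theory 1 − 0.95² = 9.75%).
- Three overall tests plus two band t-tests: 11.3–13.1%.
- The same plus two band Wilcoxon tests: 13.2–15.5%.
- Any single overall test fixed in advance: about 5% or less.

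**3. Why the methods differ.** Take a band gap of 13 min, 82 per arm, and the surgeon effects above.

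- Variance components: residual 6.5² = 42.25; surgeon 3.25² × (1 + 0.25 + 0 + 0.25 + 1)/5 = 5.28; band 13²/4 = 42.25.
- Stratified randomisation balances the bands, so the true standard error of the unadjusted difference is √(2 × 47.53/82) = 1.077.
- The unadjusted t-test estimates it as √(2 × 89.78/82) = 1.480. It rejects beyond 1.96 × 1.480 = 2.90 min, which is 2.69 true standard errors.
- Its actual size is 2 × P(Z > 2.69) = 0.7%. The simulation gave about 0.5–1% for the t-test and the Wilcoxon test.
- Power at a true 2.3 min (half the planned effect), unadjusted: P(Z > 2.69 − 2.3/1.077) = 29%. Simulation gave about 25–29% across the unadjusted tests.
- Power at 2.3 min, adjusted: standard error √(2 × 42.25/82) = 1.015, so P(Z > 1.96 − 2.3/1.015) = 62%.

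The same formulas at a 6.5-min gap give 49% against 62%, and with no gap 57% against 62%. At the planned 4.6 min and a 13-min gap they give 94% against 99.5%. In a separate simulation (4,000 trials per scenario), the three tests disagreed on significance in 17–39% of trials at 2.3 min and 2–8% at 4.6 min.

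**4. Power for an overall comparison.** A t-test for 4.6 min with SD 6.5 has 98.1% power with 66 evaluable per arm (2 × 33) and 99.5% with 82. If a win in either band were to count, Bonferroni at 0.025 per band gives 81.9% with 41 per arm per band, but 71.8% with 33.

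**The case against.** A reader might infer that the trial's real false-positive rate is well above 5%. The documents do not support that. It needs a rule that any significant result wins, and no text states one. Each overall test taken alone holds about 5% or less, and the SAP taken alone names one test for procedural time. The three overall tests share the same data and are highly correlated, so choosing among them adds at most about 3 points.

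Rates above 10% come from counting band results as primary, whereas the protocol calls that comparison secondary. A figure such as 1 − 0.95¹³ = 49% across 13 outcomes pools secondary outcomes with the primary and assumes independence; operative, fragmentation and lasing times plainly overlap. Nor is the SAP's switch to Wilcoxon a power problem in itself: at 33 per arm it has 79.0% against 80.8% for the t-test.

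The protocol can also be read as giving the t-test to the overall comparison and the MANCOVA to the secondary, by-size objective. That reading is fair and would settle the protocol internally, but the SAP would still conflict with it. Part of the SAP was not available, so a deciding rule could stand there.

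All of this limits the size of the problem. It does not reconcile the two documents.

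**Conclusion.** The conflict is real and should be resolved before the data are analysed. Three methods are named for one primary outcome, none is designated as deciding, and the unit of the sample size is left to inference. Type I error is not fixed by the plan: about 5–8% through choice among overall methods, and about 11–15% only under the unsupported assumption that a band result could also carry the primary claim.

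The more practical harm is that the unadjusted tests become conservative, and lose much power for moderate effects, when stone size strongly affects time. The direction follows from the stratified design. The amount rests on assumed band gaps and surgeon effects that the documents do not give; with no band gap the loss is small. At the planned 4.6 min the methods would usually agree, so the choice matters mainly if the true difference is smaller.

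**What to change.** In the Data Analysis section of the protocol and the Data Analysis Plan of the SAP:

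- Name one primary analysis: the laser effect on procedural time in all randomised patients, by one stated method, at two-sided 0.05. A model adjusted for size band (the randomisation stratum) and surgeon is preferable, since the protocol already intends both terms. If times are expected to be skewed, use log-transformed time or a Wilcoxon test stratified by band. Settle this before outcomes are seen by arm.
- Label the remaining methods as sensitivity analyses that do not alter the primary conclusion.
- Label band results and all other outcomes as secondary. Nominal p-values with 95% confidence intervals are acceptable.
- State whether 33 and 41 are per band, and whether the 6.5-min SD is within band or overall. Restate power for the chosen test and population: about 98% for an overall t-test with 66 evaluable per arm, 4.6 min and SD 6.5.

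The cost is a few sentences in each document. No further patients are needed for the overall comparison. What is given up is the freedom to present a secondary method or a band result as the trial's main finding.
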